#### **11.4 Analysis of Efficacy Endpoints**

The primary efficacy endpoint will be analyzed using a 2-sided Fisher Exact test and a logistic regression model to control for the stratification factors; the method of Firth will be used to predict outcomes. A 2-sided Wilcoxon rank sum test will be used to compare the distributions of scores on the 8-point WHO Ordinal Clinical Scale for the 2 treatment groups. Continuous endpoints will be evaluated using a mixed model repeated measures analysis using a compound symmetry error structure. Time to event outcomes (eg, extubation, hospital discharge, death) will be displayed using a Kaplan-Meier life table and treatment distributions compared using a stratified log-rank test and Cox proportional hazards model to control for time since diagnosis and treatment including then interaction term. A Greenwood test will be performed using the Day 28 estimates from the Kaplan-Meier lifetable.

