### **9.3 Study Design**

This is a Phase 2, randomized, placebo-controlled, multicenter study that will evaluate the efficacy, tolerability, and safety of a single dose of RBT-9 on the progression of COVID-19 infection in non-critically ill adults who are at high risk due to age and/or comorbid conditions. Subjects with documented SARS-CoV-2 infection who are at high risk for disease progression, as defined in the inclusion criteria (see [Section 9.1](#)), and require observation and/or treatment in a hospital will be screened for entry into the study. Eligible subjects will be stratified by time since COVID-19 diagnosis (<48 hours,  $\geq$ 48 hours) and randomly assigned in a 2:1 ratio to receive a single intravenous infusion of 90 mg RBT-9 or placebo (normal saline). No more than 24 hours can elapse between Screening and Dosing of RBT-9.

All subjects will be assessed through Day 56. All subjects, regardless of hospitalization status, will be assessed on Days 7, 14, 21, and 28, according to the Event Schedule (see [Section 5.1](#)). Assessments will include severity of COVID-19 measured by the 8-point WHO Ordinal Clinical Scale, physical examination, vital signs, clinical laboratory evaluations, concomitant medications, and adverse events. For subjects who have been discharged from the hospital, visits on Days 7, 14, and 21 will be conducted virtually (eg, by telephone or video contact). The Day 28 visit should be conducted in person, but may be conducted virtually, as well. Subjects will also be assessed at safety follow-up visits, which will be conducted virtually (eg, by telephone or video contact) on Days 42 and 56.

An independent data and safety monitoring board (DSMB) will actively monitor interim data to make recommendations regarding study conduct/continuation. The DSMB will meet once the first 30 subjects complete the Day 7 assessment to perform the first interim analysis of the safety data. Enrollment of 30 additional subjects will proceed if the safety profile of RBT-9 is deemed acceptable (as determined by the DSMB). Two additional DSMB interim analyses will be performed once 60 and 90 subjects complete the Day 7 evaluation. The last DSMB interim analysis will be performed once 150 subjects complete the Day 28 evaluation; sample size re-estimation will also be performed to allow a sample size increase to 252 subjects based on pre-defined conditional power rules.

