#### **11.1 Endpoints**

The following efficacy endpoints are defined for the study.

Primary Endpoint: Percentage of subjects in each treatment group in categories 4 through 8 of the 8-point WHO Ordinal Clinical Scale through Day 28.

Secondary Endpoints:

- Time to first occurrence of either death from any cause or new/worsened organ dysfunction through Day 28, defined as at least one of the following:
  - Respiratory decompensation
  - New or worsening congestive heart failure
  - Requirement of vasopressor therapy and/or inotropic or mechanical circulatory support
  - Ventricular tachycardia or fibrillation lasting at least 30 seconds and/or associated with hemodynamic instability or pulseless electrical activity, or resuscitated cardiac arrest

- Initiation of renal replacement therapy.
- Percentage of subjects who are alive at Day 28.
- Among subjects who begin oxygen therapy, mean change from initiation to last day on oxygen or Day 28 (whichever happens first) in SpO2/FiO2 ratio.
- Percentage of subjects with fever through Day 28.
- Percentage of subjects who develop AKI, as determined by the Investigator, through Day 28.
- Percentage of subjects with new or worsening congestive HF through Day 28.
- Percentage of subjects with ventricular tachycardia or fibrillation lasting at least 30 seconds and/or associated with hemodynamic instability or pulseless electrical activity, or resuscitated cardiac arrest through Day 28.
- Percentage of subjects who remain hospitalized at Day 28.
- Length of hospitalization through Day 28.
- Number of oxygen-free days through Day 28.
- Percentage of subjects transferred to the ICU through Day 28.
- Number of days on mechanical ventilation through Day 28.
- Time to and duration of vasopressor or inotrope utilization through Day 28.
- Percentage of subjects who begin dialysis through Day 28.

Exploratory Endpoints:

- Duration of COVID-19 symptoms through Day 56

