## 11.3 Data Analysis

The primary efficacy endpoint will be mapped to a binary endpoint (% categories 4-8) and then will be analyzed using a two-sided Fisher Exact test and using a logistic regression model to control for the stratification factors; the method of Firth will be used to predict outcomes. A two-sided Wilcoxon rank sum test will be used to compare the primary efficacy endpoint distributions for the two treatment groups. Continuous endpoints will be evaluated using a mixed model repeated measures (MMRM) analysis using a compound symmetry (CS) error structure. Time to event outcomes (eg, extubation, WHO progression, death) will be displayed using a Kaplan-Meier (KM) lifetable and treatment distributions compared using a stratified log-rank test and Cox proportional hazards model to control for time since COVID-19 diagnosis.

When appropriate, summary statistics will be provided (number of non-missing values, mean, median, standard deviation, minimum, and maximum for continuous variables and number and percentage of patients for categorical variables) by treatment group for all measures, including demographic and baseline assessments, safety, and efficacy endpoints. Baseline for all safety and efficacy endpoints is defined as the last observations before administration of study drug. No imputation will be used for missing data.

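### If time since diagnosis predicts outcome, the planned Wilcoxon test on the WHO scale gives up a little power by ignoring the stratum used for randomization

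*Combined protocol and SAP*

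**What the plan says.** Section 9.3 sets the randomization: "Eligible subjects will be stratified by time since COVID-19 diagnosis", with cut-points <48 h and >=48 h, and subjects are "randomly assigned in a 2:1 ratio to receive a single intravenous infusion of 90 mg RBT-9 or placebo (normal saline"). Section 9.6 confirms that sites enter this factor into the randomization system.

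The primary endpoint in section 11.1 is binary: "Percentage of subjects in each treatment group in categories 4 through 8 of the 8-point WHO Ordinal Clinical Scale through Day 28". For it, section 11.4 names a Fisher exact test and "a logistic regression model to control for the stratification factors; the method of Firth will be used to predict outcomes". Time-to-event outcomes have "treatment distributions compared using a stratified log-rank test and Cox proportional hazards model to control for time since diagnosis".

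The ordinal comparison in section 11.4 reads: "A 2-sided Wilcoxon rank sum test will be used to compare the distributions of scores on the 8-point WHO Ordinal Clinical Scale". Section 11.3 words it slightly differently: "A two-sided Wilcoxon rank sum test will be used to compare the primary efficacy endpoint distributions for the two treatment groups". The synopsis repeats the section 11.4 wording. None of the three places names a stratum for this test.

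Section 11.6 bases power on a two-group chi-square test of failure percentages. No power is stated for the Wilcoxon test. The documents give neither the expected split between the two strata nor the strength of the relation between stratum and outcome.

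**The concern.** Stratified randomization makes the two arms nearly balanced on the stratum, so differences in outcome between strata contribute almost nothing to the true sampling variance of the treatment comparison. An unstratified rank test still counts those differences as noise. If the stratum predicts outcome, the standard error is too large, the p-value is too large on average, and the test rejects less often than its nominal level allows.

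This matters because the primary objective (section 7.1) is clinical status on the 8-point scale. The Wilcoxon test is the only named comparison that uses all eight categories. It also has no stratum-controlled companion, whereas the Fisher test sits beside a logistic model that includes the factor.

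**Working it through.** **1. The plan's own figure.** Inputs from section 11.6: 84 placebo and 168 RBT-9 subjects, two-sided alpha 0.045 (z = 2.0047).

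Power = Φ[(π1 − π2 − z·SE0)/SE1], where SE0 uses the pooled proportion and SE1 the two separate proportions.

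For 25% vs 10%:
- Pooled proportion = (84×0.25 + 168×0.10)/252 = 0.15.
- SE0 = √[0.15×0.85×(1/84 + 1/168)] = 0.0477.
- SE1 = √[0.25×0.75/84 + 0.10×0.90/168] = 0.0526.
- Power = Φ[(0.15 − 2.0047×0.0477)/0.0526] = Φ(1.03) = 84.9%.

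The other two scenarios give 85.6% and 84.6%. The plan states 84%, 85% and 84%, so its figures are reproduced. The alpha split also adds up: 0.001 + 0.002 + 0.002 + 0.045 = 0.050. These figures belong to the binary endpoint and do not rest on the Wilcoxon test.

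**2. The two rank tests.** Let W be the rank sum in the RBT-9 arm, E(W) its null mean and V its tie-corrected null variance.
- Unstratified: Z = [W − E(W)]/√V over all 252 subjects.
- Van Elteren: Z = Σ{[W_h − E(W_h)]/(N_h+1)} / √Σ[V_h/(N_h+1)²], with ranks, means and variances computed within stratum h.

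**3. Simulation.** From the documents: N = 252, 2:1 allocation, two strata, two-sided 0.045, placebo failure rates of 25%, 32% and 38%, and treatment odds ratios of 0.333, 0.375 and 0.408 (powered scenarios). The odds ratio 0.545 (32% vs 20.4%) comes from the columns showing the difference that would just reach p = 0.045.

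Assumed, because the documents are silent: the spread over the eight categories, a proportional odds treatment effect, exact 2:1 allocation within strata, 15% to 50% of subjects in the <48 h stratum, better outcomes in that stratum, and a stratum odds ratio from 1 to 10. For scale, with equal strata and 32% placebo failure overall, a stratum odds ratio of 2 means about 25% vs 40% failing, and 3 means about 21% vs 45%.

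Each setting used 100,000 to 200,000 simulated trials. The Monte Carlo standard error of a Type 1 error near 0.045 is at most √(0.045×0.955/100,000) = 0.0007.

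| Stratum odds ratio | Unstratified Type 1 error | Van Elteren power gain, treatment OR 0.333-0.408 (points) | Gain, treatment OR 0.545 (points) |
|---|---|---|---|
| 1 | about 0.045 | −0.04 to +0.01 | −0.09 to −0.07 |
| 2 | 0.040-0.043 | 0.06 to 0.47 | 0.6 to 1.4 |
| 3 | 0.035-0.041 | 0.1 to 1.4 | 1.5 to 3.7 |
| 5 | 0.027-0.038 | 0.3 to 3.5 | 2.8 to 8.2 |
| 10 | 0.015-0.033 | 0.4 to 9.2 | 4.4 to 17.0 |

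The van Elteren Type 1 error stays at about 0.044-0.047 throughout.

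**4. Reading the table.** With equal strata, 32% placebo failure and a stratum odds ratio of 3, the simulated Type 1 error is 0.0352. That corresponds to a critical value of 2.106 on the correct scale, against the nominal 2.005, so the unstratified standard error is about 5% too large (2.106/2.005 = 1.05). The power cost is small at the design effects because the ordinal test is already near its ceiling. At treatment odds ratio 0.375 with equal strata, power is 96.4% unstratified and 96.7% stratified at stratum odds ratio 2, and 95.5% and 96.4% at 3. At odds ratio 0.545 there is more room: 65.7% vs 67.1% and 62.4% vs 66.1%.

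**5. Effect in one stratum only.** With treatment odds ratio 0.375 confined to the >=48 h stratum, van Elteren changes power by −0.5 to +0.4 points. Confined to the <48 h stratum, it gains 0 to 7 points (stratum odds ratio 1 to 3).

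**The case against.** Four points can be made for leaving the plan alone.

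- **The loss is conditional.** A reader might infer that the test is conservative simply because it omits the stratum. It is not: with a stratum odds ratio of 1 both tests hold their level and have the same power. The documents give no evidence on the strength of the stratum. This stands, and the point is therefore stated conditionally.
- **The test carries no stated weight.** A reader might infer that the trial's power or error control is at risk. Sizing, interim rules and the primary endpoint all rest on the percentage in categories 4 to 8, and conservatism does not inflate Type 1 error. This also stands.
- **The Wilcoxon test is not alone.** The Fisher test, named first for the primary endpoint, is also unstratified. That is true, but the logistic model beside it controls for the factor.
- **Detail is deferred.** Section 11 leaves full detail to a separate SAP. But the protocol already names this test in three places, and a later SAP would have to depart from it.

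A reader might also extend the criticism to "A Greenwood test will be performed using the Day 28 estimates from the Kaplan-Meier lifetable". Section 11.4 does not say whether those estimates are pooled or taken by stratum, so silence is not evidence that the comparison is unstratified. No size was worked out for it, and it is no part of this point.

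**Conclusion.** The mismatch is real and minor. The plan randomizes within time-since-diagnosis groups and uses them in three neighbouring analyses, but not in its only full-scale ordinal comparison.

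Whether this costs anything depends on the prognostic strength of the stratum, which is unknown. For a stratum odds ratio of 2 to 3, the cost is at most about half a point to 1.4 points of power at the design effects, and up to 3.7 points at odds ratio 0.545. It becomes material only with a stratum odds ratio of about 5 or more, or with a weaker treatment effect. These sizes rest on the assumed category spread, stratum split and proportional odds.

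The primary analysis, its 84-85% power and the overall 5% error rate are untouched.

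**What to change.** In the synopsis and sections 11.3 and 11.4, replace the Wilcoxon rank sum test by a two-sided van Elteren test of the 8-point WHO scores, stratified by the time-since-diagnosis group used at randomization. Use the same wording in all three places, so that section 11.3 also refers to the scale scores. Make the change before any unblinded outcome data are seen.

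The cost is one line of text and standard software. The statistical downside is negligible but not zero: up to about 0.1 point of power if the stratum is not prognostic, and up to about 0.5 point if the effect is confined to the >=48 h stratum. No change to the sample size, alpha split or primary analysis is needed.

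### The repeated-measures model with compound symmetry named for continuous endpoints does not fit any listed continuous efficacy endpoint, because each is a single value per subject.

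*Combined protocol and SAP*

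**What the plan says.** The rule for continuous endpoints appears three times. Section 11.4 states: "Continuous endpoints will be evaluated using a mixed model repeated measures analysis using a compound symmetry error structure". Section 11.3 states: "Continuous endpoints will be evaluated using a mixed model repeated measures (MMRM) analysis using a compound symmetry (CS) error structure". The efficacy paragraph of the synopsis (Section 4, Statistics) matches Section 11.4. None of the three names a response variable, visits, fixed effects, covariates, an alternative covariance structure or robust standard errors.

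The efficacy endpoints in Section 11.1 that are neither percentages nor purely times to an event are:

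- SpO2/FiO2 ratio, only in subjects who start oxygen, as "mean change from initiation to last day on oxygen or Day 28 (whichever happens first")
- "Length of hospitalization through Day 28"
- "Number of oxygen-free days through Day 28"
- "Number of days on mechanical ventilation through Day 28"
- the duration part of "Time to and duration of vasopressor or inotrope utilization through Day 28"
- exploratory: "Duration of COVID-19 symptoms through Day 56"

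Section 11.4 separately sends time-to-event outcomes to Kaplan-Meier, stratified log-rank and Cox methods, giving extubation, hospital discharge and death as examples. Section 11.5 has vital signs and laboratory values summarised descriptively. The opening of Section 11 leaves full detail to a separate SAP, whose text is not part of the document reviewed.

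**The concern.** A repeated-measures model needs several values per subject. If each endpoint gives one, the plan has named a method that cannot be applied as written. The analyst must then pick another, possibly after seeing the data. The nearest literal reading is a plain comparison of two means with no adjustment for the randomisation stratum, since none is stated for these endpoints. That suits the day counts poorly. They are bounded by the follow-up window, and ventilator and vasopressor days should be zero for many subjects in a population that is not critically ill at entry. A mean difference would then rest on few subjects. Death also distorts these counts: a subject who dies early accrues few ventilator or hospital days and would look like a success.

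The covariance choice raises a second, conditional question. Compound symmetry forces one variance and one correlation across visits. It matters only if a by-visit measure is modelled.

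**Working it through.** **1. Figures in the plan.** The plan gives no SD, correlation or sample size for any continuous endpoint. Its only power figures, in Section 11.6, are for the binary primary endpoint. They reproduce with the pooled-variance normal approximation (84 versus 168, two-sided 0.045, no continuity correction):

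| Placebo vs RBT-9 | Stated | Recomputed |
|---|---|---|
| 25% vs 10% | 84% | 84.9% |
| 32% vs 15% | 85% | 85.6% |
| 38% vs 20% | 84% | 84.6% |

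Nothing below changes them.

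**2. Values per subject.** Each endpoint listed above is a total, a duration or one change score, so each gives one value. None is defined by visit. SpO2 and FiO2 are recorded at several visits (Sections 5.1 and 9.10.4), but the endpoint runs between dates that differ by subject, so a by-visit model would not estimate it.

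**3. The named model with one value per subject.** Compound symmetry splits the total variance into a between-subject and a within-subject part. One value per subject informs only their sum. As a check, one standard-normal value per subject was simulated for 84 and 168 subjects:

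- Ordinary least squares: difference -0.01345, SE 0.1229. Implied variance = 0.1229² / (1/84 + 1/168) = 0.0151 / 0.01786 = 0.845.
- Random-intercept model: the same difference, with the variance split 0.423 + 0.423 = 0.845 and a warning that the Hessian was not positive definite.

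The total agrees, the split is arbitrary, and the SE printed by that fit (0.110) should not be relied on. The model reduces to a comparison of two means.

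**4. Compound symmetry if a measure were analysed by visit (illustration).** The visit SDs are assumptions. Take complete data at four visits, treatment-by-visit means, and the same covariance in both arms. In large samples:

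- SE ratio at the last visit = √(mean of visit variances) / (last-visit SD)
- type I error = 2[1 − Φ(1.96 × ratio)]
- power, where 80% is intended = Φ(2.80 − 1.96 × ratio)

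| SD over four visits (linear) | Mean variance | SE ratio, last visit | Consequence |
|---|---|---|---|
| 1.0 to 1.3 | 1.335 | 1.155/1.3 = 0.89 | type I error 8.2% |
| 1.0 to 1.6 | 1.740 | 1.319/1.6 = 0.82 | type I error 10.6% |
| 1.3 to 1.0 | 1.335 | 1.155/1.0 = 1.16 | power 70% |
| 1.6 to 1.0 | 1.740 | 1.319/1.0 = 1.32 | power 59% |

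Equal SDs with an equal correlation of 0.5 give a ratio of 1.00. Equal SDs with AR(1) correlation 0.7 give 1.00 at each visit but 0.81 for the first-to-last change (type I error 11.3%). The treatment difference averaged over visits has ratio 1.00 in every scenario run.

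**5. Size of the SpO2/FiO2 subset.** Assume, roughly, that subjects who start oxygen match the primary failure rates in Section 11.6. At 252 subjects:

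- 25%/10%: 84 × 0.25 + 168 × 0.10 = 21.0 + 16.8 ≈ 38
- 38%/20%: 84 × 0.38 + 168 × 0.20 = 31.9 + 33.6 ≈ 66

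**The case against.** **Time-to-event methods already cover part of this.** Partly right. Section 11.4 names hospital discharge and extubation, which bear on hospital stay and ventilation, and the time to vasopressor use is a time-to-event outcome. But the plan does not say that these replace the continuous analysis of hospital or ventilator days. Oxygen-free days, vasopressor duration, the SpO2/FiO2 change and symptom duration have no other stated method.

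**The separate SAP would supply the detail.** Model terms could reasonably wait for it. The protocol, however, already fixes both the model and the covariance structure, in three places. That is a stated method that does not fit, not just an omission.

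**A comparison of means at 84 versus 168 may behave acceptably.** This stands as a limit. No inflated error has been shown for the single-value endpoints. The objection to the default is poor fit and lack of pre-specification. Nor are all the endpoints zero-heavy counts: the SpO2/FiO2 change is a change in a ratio, and hospital days are not shown to pile up at zero, since admission is an entry criterion.

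**A stronger reading.** A reader might infer that compound symmetry makes the trial's Day 28 standard errors and p-values wrong. The documents do not support that. No listed continuous efficacy endpoint is analysed by visit, vital signs are only described, and no visit variances are given. The table in step 4 shows what could happen if a by-visit analysis were added; it does not describe a planned test.

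**Conclusion.** The point holds as a mismatch between method and endpoint. Five secondary endpoints and one exploratory endpoint are assigned to a model that cannot be fitted to them as a repeated-measures model, and most have no alternative named. This follows from the text alone and needs no assumed figures. It should be corrected, but it does not touch the primary analysis, its power, the sample size or the alpha plan.

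The covariance point is conditional. Compound symmetry can misstate standard errors for visit-specific or change contrasts, in either direction, if a by-visit measure is modelled and variances or correlations are unequal. The 8-11% type I error rests wholly on assumed SDs. There is no misstatement if compound symmetry is true, and none was found for the average over visits.

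**What to change.** Replace the sentence in the synopsis, Section 11.3 and Section 11.4, and carry the new text into the SAP:

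- **Day-count and duration endpoints** (hospital, oxygen-free, ventilator, vasopressor or inotrope, symptoms): Wilcoxon (van Elteren) test stratified by time since diagnosis, with deaths given a pre-stated worst rank. Report a mean difference with a bootstrap interval. A Hodges-Lehmann shift is less useful here, because it can be exactly zero when many values are zero.
- **SpO2/FiO2 change:** ANCOVA with the value at oxygen initiation and the stratum as covariates, in subjects who start oxygen.
- **Hospital stay and ventilation:** state how these analyses relate to the time-to-event analyses of discharge and extubation.
- **Any measure analysed by visit:** name the response, visits and covariates. Use an unstructured covariance with a pre-stated fallback or robust standard errors.

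The cost is a wording change to the protocol as well as the SAP, plus slightly more analysis work. Data collection, sample size and alpha do not change. An unstructured covariance at four visits has 10 parameters (4 variances and 6 covariances) against 2 for compound symmetry. That is minor at 252 subjects, but in a by-visit SpO2/FiO2 analysis of roughly 38 to 66 subjects, on the assumption in step 5, the fallback may be needed.

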**Statistics continued:**

**Efficacy Analysis:** The primary efficacy endpoint will be analyzed using a 2-sided Fisher Exact test and a logistic regression model to control for the stratification factor (time since COVID-19 diagnosis); the method of Firth will be used to predict outcomes. A 2-sided Wilcoxon rank sum test will be used to compare the distributions of scores on the 8-point WHO Ordinal Clinical Scale for the 2 treatment groups. Continuous endpoints will be evaluated using a mixed model repeated measures analysis using a compound symmetry error structure. Time to event outcomes (e.g., extubation, hospital discharge, death) will be displayed using a Kaplan-Meier life table and treatment distributions compared using a stratified log-rank test and Cox proportional hazards model to control for time since diagnosis and treatment including the interaction term. A Greenwood test will be performed using the Day 28 estimates from the Kaplan-Meier lifetable.

**Safety Analysis:** Safety measures including adverse events, clinical laboratory tests, vital signs, physical examinations, and concomitant medication usage will be summarized descriptively by treatment group.

When appropriate, summary statistics will be provided (number of non-missing values, mean, median, standard deviation, minimum, and maximum for continuous variables and number and percentage of patients for categorical variables) by treatment group for all measures, including demographic and baseline assessments, safety, and efficacy endpoints. Baseline for all safety and efficacy endpoints is defined as the last observations before administration of study drug. No imputation will be used for missing data.

**Interim Analyses:** A group sequential design will be conducted with 4 pre-planned interim analyses after 30, 60, and 90 subjects complete the Day 7 evaluation and 150 subjects complete the Day 28 evaluation. At each interim, the DSMB will evaluate an independently conducted analysis in order to assess safety and futility.

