### **11 STATISTICAL CONSIDERATIONS**

This section outlines the nature and rationale for the statistical methods to be used for the study design and analysis. A separate Statistical Analysis Plan will describe data handling and statistical techniques in full detail.

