## 12 WITHDRAWAL FROM STUDY

Every reasonable effort should be made to maintain protocol compliance and participation in the study. Should a subject withdraw or be prematurely terminated from the study for any reason, the reason for early study withdrawal will be recorded. If withdrawal is the result of a serious adverse reaction, the subject will be followed until the condition has resolved, as determined by the Investigator.

The Investigator or Sponsor may withdraw any subject at any time for medical reasons or for administrative reasons (ie, subjects unable or unwilling to comply with the protocol). If so, the subject will be censored at time of withdrawal and, if possible, a final evaluation (End of Study procedures) will be made. All treated subjects will be included in the safety analyses.

In the unlikely event the Sponsor or FDA should determine it is appropriate to terminate the study early, every effort will be made for transitioning subjects with minimal disruption to the subject and Investigator. The IRB will be notified of termination, and reason(s) and procedures for follow-up of research subjects will be developed by the study physician in consultation with the Sponsor and IRB.

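### No rule says how deaths are coded in the Kaplan-Meier analyses of discharge, extubation and vasopressor or inotrope start; if deaths are censored, the Day 28 probabilities of these events are overstated

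*Combined protocol and SAP*

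**What the plan says.** Section 11.4 puts two non-fatal events and death under one method: "Time to event outcomes (eg, extubation, hospital discharge, death) will be displayed using a Kaplan-Meier life table". The comparison follows in the same sentence: "treatment distributions compared using a stratified log-rank test and Cox proportional hazards model to control for time since diagnosis and treatment". Section 11.4 and the synopsis (Section 4, Statistics) both add: "A Greenwood test will be performed using the Day 28 estimates from the Kaplan-Meier lifetable". Neither limits that test to particular outcomes.

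Section 11.3 has a parallel sentence with different examples: "Time to event outcomes (eg, extubation, WHO progression, death) will be displayed using a Kaplan-Meier (KM) lifetable". Extubation is in both lists; hospital discharge is only in Section 11.4 and the synopsis.

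The endpoint list in Section 11.1 contains neither time to discharge nor time to extubation. It has length of hospital stay and days on mechanical ventilation instead. It does list one purely non-fatal time-to-event endpoint, the time to starting a vasopressor or inotrope.

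The only censoring rule is in Section 12 and concerns withdrawal: "the subject will be censored at time of withdrawal". Nothing mentions competing events or cumulative incidence, or says how a death enters the analysis of a non-fatal event. Section 11 defers detail: "A separate Statistical Analysis Plan will describe data handling and statistical techniques in full detail".

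**The concern.** A subject who dies in hospital cannot later be discharged alive, extubated or started on a vasopressor. Kaplan-Meier assumes that a censored subject could still have the event, at the same rate as those still under observation. Censoring a death therefore shares that subject's weight among the survivors and credits the dead with events that they cannot have. The complement of the curve at Day 28 then no longer estimates the proportion of randomised subjects who had the event, yet the Greenwood test compares exactly that quantity between arms.

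Two things are at stake. Each arm's Day 28 figure could be too high. And two arms with the same daily discharge rate but different mortality would show the same discharge curve, so a table of discharge results could look neutral beside an excess of deaths.

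Extubation has a further difficulty. It is defined only among intubated subjects, a group formed after randomisation that treatment may change, so a comparison within it is not a randomised comparison.

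**Working it through.** **Inputs.** The protocol gives no discharge, extubation, vasopressor or mortality rate, and no figure for any of these analyses, so there is nothing to reproduce. All rates below are assumptions, taken as constant daily hazards over 28 days: h_k for the non-fatal event and h_d for death before it.

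**Formulas.**
- Proportion who truly have the event by Day 28: F_k = h_k/(h_k + h_d) × [1 − exp(−28(h_k + h_d))].
- Kaplan-Meier complement with deaths censored at death: 1 − exp(−28 h_k).
- From assumed Day 28 shares F_k and F_d: 28(h_k + h_d) = −ln(1 − F_k − F_d), and 28 h_k is the fraction F_k/(F_k + F_d) of that.

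**Step 1: overstatement within one arm.** Example with 75% discharged and 20% dead first: −ln(0.05) = 2.996; × 0.75/0.95 = 2.365; 1 − exp(−2.365) = 0.906, against a true 0.75.

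| Event | Die first | True Day 28 share | Kaplan-Meier, deaths censored | Excess (points) |
|---|---|---|---|---|
| Discharge | 2% | 95% | 96.8% | 1.8 |
| Discharge | 5% | 90% | 94.2% | 4.2 |
| Discharge | 10% | 85% | 93.2% | 8.2 |
| Discharge | 20% | 75% | 90.6% | 15.6 |
| Extubation | 40% | 40% | 55.3% | 15.3 |

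The 20% row is an upper end. Section 11.6 assumes total failure, death included, of 25% to 38% on placebo and 10% to 20% on RBT-9.

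**Step 2: when the event is uncommon.** Write x = 28 h_k and y = 28 h_d. For small x and y, the excess 1 − exp(−x) − [x/(x + y)][1 − exp(−(x + y))] is about xy/2. So if few subjects start a vasopressor and few die without one, the error is small. The gap in the rule is the same; its effect is largest for discharge and extubation.

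**Step 3: difference between arms.** Take a discharge hazard of 0.10 per day in both arms. The Kaplan-Meier complement is 1 − exp(−2.8) = 93.9% whatever the mortality.

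| Death hazard per day | Truly discharged | Dead before discharge | Kaplan-Meier, deaths censored |
|---|---|---|---|
| 0.005 | 90.2% | 4.5% | 93.9% |
| 0.015 | 83.5% | 12.5% | 93.9% |
| 0.0125 | 85.1% | 10.6% | 93.9% |
| 0.025 | 77.6% | 19.4% | 93.9% |

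Comparing 0.005 with 0.015, a true gap of 90.2 − 83.5 = 6.7 points appears as zero. Comparing 0.0125 with 0.025, the hidden gap is 85.1 − 77.6 = 7.5 points.

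**Step 4: simulation.** 400 runs with 84 placebo and 168 RBT-9 subjects, death hazards 0.005 and 0.015, events recorded by whole day with same-day ties counted as discharge.
- Deaths censored at death: mean Kaplan-Meier discharge 94.1% and 93.9%; log-rank rejects in 4.8% of runs at 0.05.
- Deaths kept in the risk set past Day 28: 90.6% and 84.0%; log-rank rejects in 14.0%.

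The second coding recovers the true proportions closely and makes the difference visible. The coding of deaths decides the result.

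**The case against.** The strongest reply is that the bias is not in the text. Nothing says that deaths are censored at death. Kaplan-Meier with deaths carried to Day 28 as not discharged fits the same sentence and has no overstatement, and Section 11 leaves data handling to a separate plan. This stands in part: it is not established that the estimates will be wrong. But the correct coding needs an explicit rule, none is given, and the ordinary application of the named method censors at death.

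A reader might infer that the trial would hide excess deaths. The documents do not support that. Death is category 8 of the scale in the primary endpoint ("Percentage of subjects in each treatment group in categories 4 through 8 of the 8-point WHO Ordinal Clinical Scale through Day 28"), part of the composite time-to-event endpoint, a secondary endpoint in its own right ("Percentage of subjects who are alive at Day 28") and a Kaplan-Meier outcome in the sentence at issue. The loss is confined to the non-fatal curves.

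A reader might also infer that the log-rank test and Cox model are invalid. They are not. With deaths censored, both validly compare cause-specific hazards; they do not compare Day 28 probabilities.

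Discharge and extubation are illustrative examples, not listed endpoints, and the Greenwood test may have been meant only for death or the composite, where it is sound. Both points lower the importance. They do not close the gap, because the test is written without restriction and vasopressor or inotrope start is a listed endpoint.

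**Conclusion.** The protocol applies Kaplan-Meier to events that death precludes and adds an unrestricted Day 28 comparison of those estimates, without saying how deaths are coded. If deaths are censored at death, the Day 28 discharge probability is overstated by about 2 points when 2% die first and about 16 points when 20% do, and a mortality difference between arms disappears from those curves. If deaths are carried to Day 28 as event-free, the overstatement is zero. The sizes rest on assumed constant hazards, since the documents give no rates, and the effect is smaller for uncommon events such as vasopressor start.

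This is a secondary-level point. The primary analysis uses a binary endpoint that counts death as failure, so sample size, alpha and the stopping rules are untouched.

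**What to change.** In Sections 4, 11.3 and 11.4, and in the separate analysis plan:

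- State for each non-fatal time-to-event outcome how a death is coded.
- For discharge, extubation and vasopressor or inotrope start, replace the Day 28 Kaplan-Meier and Greenwood comparison with Aalen-Johansen cumulative incidence, death as a competing event, and a Gray test stratified by time since diagnosis. Show the cumulative incidence of death beside it.
- For discharge and extubation, carrying deaths to Day 28 as event-free is an equivalent choice when nobody withdraws earlier. For vasopressor or inotrope start, cumulative incidence is preferable, because there event-free would read as a good outcome for someone who died.
- Keep the log-rank test and Cox model if they are labelled as cause-specific hazard comparisons.
- Keep Kaplan-Meier and Greenwood for death and for composites that include death, and say that the Greenwood test is limited to these.
- Report time to extubation among intubated subjects descriptively only.

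The cost is wording and standard software. The listed endpoints on stay, ventilation, vasopressor use and survival already need the relevant dates, so no new data are required.
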